10. STUDY GOVERNANCE CONSIDERATIONS

10.1. Posting of Information on Publicly Available Clinical Trials Registers

Study information from this protocol will be posted on publicly available clinical trial registers before enrollment of subjects begins.

10.2. Regulatory and Ethical Considerations, Including the Informed Consent

The study will be conducted in accordance with all applicable regulatory requirements, and with GSK policy.

 GlaxoSmithKline	Document Name	207656 Clinical Protocol		
	Type	Version	Document Identifier	Effective Date
	eldo_clinical_doc	3.0; Most-Recent; Effective; CURRENT	090032d580d46916	25-May-2017 00:11:53
	Reason For Issue	Auto Issue		

The study will also be conducted in accordance with ICH Good Clinical Practice (GCP), all applicable subject privacy requirements, and the guiding principles of the current version of the Declaration of Helsinki. This includes, but is not limited to, the following:

- Before initiating a trial, the investigator should have written and dated approval/favourable opinion from the IEC for the trial protocol (including amendments), written informed consent form, consent form updates, subject recruitment procedures (e.g., advertisements), safety statement (including any updates) and any other written information to be provided to subjects. A letter or certificate of approval will be sent by the investigator to the sponsor prior to initiation of the study, and also when subsequent amendments to the protocol are made.
- Signed informed consent to be obtained for each subject before participation in the study (and for amendments as applicable)
- Investigator reporting requirements (e.g. reporting of AEs/SAEs/protocol deviations to IEC)
- GSK will provide full details of the above procedures, either verbally, in writing, or both.

10.3. Quality Control (Study Monitoring)

In accordance with applicable regulations including GCP, and GSK procedures, the study monitor will contact the site prior to the start of the study to review with the site staff the protocol, study requirements, and their responsibilities to satisfy regulatory, ethical, and GSK requirements.

When reviewing data collection procedures, the discussion will include identification, agreement and documentation of data items for which the eCRF will serve as the source document.

The study monitor will monitor the study and site activity to verify that the:

- Data are authentic, accurate, and complete.
- Safety and rights of subjects are being protected.
- Study is conducted in accordance with the currently approved protocol and any other study agreements, GCP, and all applicable regulatory requirements.

The extent and nature of monitoring will be described in a written monitoring plan on file at the third party CRO. The investigator (or designee) agrees to allow the monitor direct access to all relevant documents and agrees to co-operate with the monitor to ensure that any problems detected in the course of these monitoring visits are resolved.

 GlaxoSmithKline	Document Name	207656 Clinical Protocol		
	Type	Version	Document Identifier	Effective Date
	eldo_clinical_doc	3.0; Most-Recent; Effective; CURRENT	090032d580d46916	25-May-2017 00:11:53
	Reason For Issue	Auto Issue		

10.4. Quality Assurance

To ensure compliance with GCP and all applicable regulatory requirements, GSK may conduct a quality assurance assessment and/or audit of the site records, and the regulatory agencies may conduct a regulatory inspection at any time during or after completion of the study.

In the event of an assessment, audit or inspection, the investigator (and institution) must agree to grant the advisor(s), auditor(s) and inspector(s) direct access to all relevant documents and to allocate their time and the time of their staff to discuss the conduct of the study, any findings/relevant issues and to implement any corrective and/or preventative actions to address any findings/issues identified.

The sponsor will be available to help investigators prepare for an inspection.

10.5. Conditions for Terminating the Study

Upon completion or premature discontinuation of the study, the study monitor will conduct site closure activities with the investigator or site staff, as appropriate, in accordance with applicable regulations including GCP, GSKCH Standard Operating Procedures (SOPs), and the third party CRO SOPs.

Both GSKCH and the Investigator reserve the right to temporarily suspend or prematurely discontinue this study at any time for reasons including, but not limited to, safety or ethical issues or severe non-compliance.

If the trial is prematurely terminated or suspended for any reason, the investigator site should promptly inform the trial subjects and should assure appropriate therapy/ follow-up for the subjects.

In addition:

- If the investigator terminates or suspends a trial without prior agreement of GSKCH, the investigator site should promptly inform the sponsor and the IEC, and should provide the sponsor and the IEC a detailed written explanation of the termination or suspension.
- If the GSKCH terminates or suspends a trial, the investigator should promptly inform the IEC and provide the IEC a detailed written explanation of the termination or suspension.
- If the IEC terminates or suspends its approval/favourable opinion of a trial, the investigator should promptly notify the GSKCH and provide GSKCH with a detailed written explanation of the termination or suspension.

 GlaxoSmithKline	Document Name	207656 Clinical Protocol		
	Type	Version	Document Identifier	Effective Date
	eldo_clinical_doc	3.0; Most-Recent; Effective; CURRENT	090032d580d46916	25-May-2017 00:11:53
	Reason For Issue	Auto Issue		

10.6. Records Retention

Following closure of the study, the investigator must maintain all site study records (except for those required by local regulations to be maintained elsewhere), in a safe and secure location.

The records (study/ site master file) must be maintained to allow easy and timely retrieval, when needed (e.g., for a GSK audit or regulatory inspection) and must be available for review in conjunction with assessment of the facility, supporting systems, and relevant site staff.

Where permitted by local laws/regulations or institutional policy, some or all of these records can be maintained in a format other than hard copy (e.g., microfiche, scanned, electronic); however, caution needs to be exercised before such action is taken.

The investigator must ensure that all reproductions are legible and are a true and accurate copy of the original and meet accessibility and retrieval standards, including re-generating a hard copy, if required. Furthermore, the investigator must ensure there is an acceptable back-up of these reproductions and that an acceptable quality control process exists for making these reproductions.

The investigator must assure that the subject's anonymity will be maintained on eCRFs or other documents submitted to inVentiv Health, GSKCH, or any other GSKCH approved vendors. Subjects should not be identified by their names or initials, but by an identification code. The investigator should keep a separate log of subjects' codes, names and addresses. Documents not for submission to inVentiv Health, GSKCH, or any other GSKCH approved vendors, e.g. subjects' written consent forms, should be maintained by the investigator in strict confidence.

GSKCH will inform the investigator of the time period for retaining these records to comply with all applicable regulatory requirements (GSKCH recommends that documents be kept for 10 years). The investigator is also required to keep subject identification codes on file for at least 15 years after completion or discontinuation of the study. The minimum retention time will meet the strictest standard applicable to that site for the study, as dictated by any institutional requirements or local laws or regulations, GSKCH standards/procedures, and/or institutional requirements.

No study document should be destroyed without a prior written agreement between GSKCH and the investigator. The investigator must notify GSKCH of any changes in the archival arrangements, including, but not limited to, archival at an off-site facility

 GlaxoSmithKline	Document Name	207656 Clinical Protocol		
	Type	Version	Document Identifier	Effective Date
	eldo_clinical_doc	3.0; Most-Recent; Effective; CURRENT	090032d580d46916	25-May-2017 00:11:53
	Reason For Issue	Auto Issue		

or transfer of ownership of the records in the event the investigator is no longer associated with the site.

10.7. Provision of Study Results to Investigators, posting of Information on Publicly Available Clinical Trials Registers and Publication

Where required by applicable regulatory requirements, an investigator signatory will be identified for the approval of the clinical study report. The investigator will be provided reasonable access to statistical tables, figures, and relevant reports and will have the opportunity to review the complete study results at a GSK site or other mutually-agreeable location.

GSKCH will also provide the investigator with the full summary of the study results. The investigator is encouraged to share the summary results with the study subjects, as appropriate.

The procedures and timing for public disclosure of the results summary and for development of a manuscript for publication will be in accordance with GSK Policy.

A manuscript will be progressed for publication in the scientific literature if the results provide important scientific or medical knowledge.

 GlaxoSmithKline	Document Name	207656 Clinical Protocol		
	Type	Version	Document Identifier	Effective Date
	eldo_clinical_doc	3.0; Most-Recent; Effective; CURRENT	090032d580d46916	25-May-2017 00:11:53
	Reason For Issue	Auto Issue		

	Attachment 1: List of Data Displays	22
	Appendix 1: Templates for Tables, Figures & Listings	23

Abbreviation

AE	Adverse Event
ANCOVA	Analysis Of Covariance
BDRM	Blinded Data Review Meeting
CI	Confidence Interval
DH	Dentinal Hypersensitivity
EAR	Erosion, Abrasion, Recession
eCRF	Electronic Case Report Form
GSK CH	Glaxosmithkline Consumer Healthcare
ITT	Intent-To-Treat
MedDRA	Medical Dictionary For Regulatory
N	Number Of Subjects
OHT	Oral Hard Tissue
OST	Oral Soft Tissue
PP	Per Protocol
ppm	Parts Per Million
RAP	Reporting And Analysis Plan
RLR	Review Listing Requirement
SAE	Serious Adverse Event
SAP	Statistical Analysis Plan
SD	Standard Deviation
SEs	Standard Error
SMS	Short Service Message
SOC	System Organ Class
VRS	Visual Rating Scale
w/w	Weight/Weight

The purpose of this Statistical Reporting and Analysis Plan is to describe the planned analyses and outputs to be included in the Clinical Study Report for Protocol 207656.

1 Summary of Key Protocol Information

The purpose of this trial is to demonstrate the efficacy and safety of a 1.5% dipotassium oxalate monohydrate (KOX) containing oral rinse to treat the symptoms of Dental Hypersensitivity (DH). Efficacy will be demonstrated as a treatment difference in favour of the 1.5% KOX containing oral rinse vs. the negative control oral rinse for the primary efficacy outcome, Schiff sensitivity score at Week 8. Safety will be demonstrated through assessment of adverse events (AEs).

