	Type	Version	Document Identifier	Effective Date
	eldo_clinical_doc	3.0; Most-Recent; Effective; CURRENT	090032d580d46916	25-May-2017 00:11:53
	Reason For Issue	Auto Issue		

PROTOCOL SYNOPSIS FOR STUDY 207656

Brief Summary

This single centre, randomised, examiner blind, three-treatment arm, parallel design method development study will be used to investigate the efficacy of an experimental oral rinse, containing 1.5% potassium oxalate (KOX) and 0 ppm fluoride in relieving dentine hypersensitivity (DH) after 8 weeks use compared with a placebo oral rinse and a commercialised fluoride oral rinse.

The study will be conducted in healthy subjects with pre-existing self-reported and clinically diagnosed tooth sensitivity at screening.

Objectives and Endpoints

Objectives	Endpoints
Primary	

 To evaluate and compare the clinical efficacy of a 1.5% KOX containing oral rinse for the relief of DH, as elicited by an evaporative air stimulus (with Schiff Sensitivity Scale), against a negative control oral rinse, following use as an adjunct to twice daily brushing with a standard fluoride dentifrice, after 8 weeks. 	
 Change from baseline in Schiff sensitivity score at 8 weeks.
Secondary	

 To evaluate and compare the clinical efficacy of a 1.5% KOX containing oral rinse for the relief of DH, as elicited by a tactile stimulus (Yeaple probe), against a negative control oral rinse, following use as an adjunct to twice daily brushing with a standard fluoride dentifrice, after 8 weeks. 	
 Change from baseline in tactile threshold (Yeaple probe) at 8 weeks.

 GlaxoSmithKline	Document Name	207656 Clinical Protocol		
	Type	Version	Document Identifier	Effective Date
	eldo_clinical_doc	3.0; Most-Recent; Effective; CURRENT	090032d580d46916	25-May-2017 00:11:53
	Reason For Issue	Auto Issue		

Exploratory	

 To evaluate and compare the clinical efficacy of a 1.5% KOX containing oral rinse for the relief of DH, as elicited by an evaporative air stimulus (with Schiff Sensitivity Scale), against a placebo oral rinse, following use as an adjunct to twice daily brushing with a standard fluoride dentifrice, after 8 weeks. 	
 Change from baseline in Schiff sensitivity score at 8 weeks.

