- Review of completed diary and weight of oral rinse bottle and contents will be

 GlaxoSmithKline	Document Name	207656 Clinical Protocol		
	Type	Version	Document Identifier	Effective Date
	eldo_clinical_doc	3.0; Most-Recent; Effective; CURRENT	090032d580d46916	25-May-2017 00:11:53
	Reason For Issue	Auto Issue		

checked to determine usage compliance.

- A supervised brushing and rinse will be conducted, subjects will be requested to measure out the dose of the oral rinse using the dosing cup provided.
- Study kit returned to subject.
- AEs and incidents following supervised brushing and rinse.
- Confirmation of subject continuance.

Visit 10 - Week 8/ LSLV

The following assessments will be conducted:

- Review of current/concomitant medications, AEs and incidents.
- Return of study kit.
- Review of completed diary and weight of oral rinse bottle and contents will be checked to determine usage compliance.
- Confirmation of subject continuance.
- OST examination.
- Tactile sensitivity assessment of two eligible test teeth.
- Evaporative air sensitivity assessment of two eligible test teeth (Schiff sensitivity score and VRS).
- Subjects return all study products.
- Completion of compliance check.

Type and Planned Number of Subjects

A sufficient number of healthy subjects will be screened to randomise at least 100 subjects (approximately 50 to the experimental treatment, 25 to the negative control and 25 to placebo) to ensure 80 evaluable subjects complete the entire study. This will ensure approximately 40 evaluable subjects for the test treatment and 20 each for the negative control treatment and placebo.

With this 40/20/20 distribution of the subjects in the treatment arms, the study has less than 50% power to detect a mean treatment difference of 0.36 in the Schiff sensitivity score using a two-sided t-test of significance level 0.05 for the experimental product against the negative control. The standard deviation used in this calculation is 0.8; this estimate is obtained from the GSKCH study 204763. When the experimental treatment group is compared with the combined group comprising of the negative control group and the placebo group using the two-sided t-test with the same estimates of mean difference, significance level and standard deviation, the study will have 51.1% power.

 GlaxoSmithKline	Document Name	207656 Clinical Protocol		
	Type	Version	Document Identifier	Effective Date

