9.2.4. Criteria for Assessing Efficacy

The primary treatment comparison is between the experimental mouthwash and the negative control marketed mouthwash for the change from baseline in the Schiff Sensitivity score at 8 weeks. However a statistically significant difference is not expected as the study is not powered. The magnitude of the treatment difference is more important and is expected to be in favour of the experimental mouthwash.

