1.4 Sample Size Calculation

A sufficient number of healthy subjects will be screened to randomise at least 100 subjects (approximately 50 to the experimental treatment, 25 to the negative control and 25 to placebo) to ensure 80 evaluable subjects complete the entire study. This will ensure approximately 40 evaluable subjects for the test treatment and 20 each for the negative control treatment and placebo.

With this 2:1:1 distribution of the subjects in the treatment arms, the study has less than 50% power to detect a mean treatment difference of 0.36 in the Schiff sensitivity score using a two-sided t-test of significance level 0.05 for the experimental product against the negative control. The standard deviation used in this calculation is 0.8; this estimate is obtained from the GSKCH study 204763. When the experimental treatment group is compared with the combined group comprising of the negative control group and the placebo group using the two-sided t-test with the same estimates of mean difference, significance level and standard deviation, the study will have 51.1% power.

The magnitude of the treatment difference is more important and is expected to be in favour of the experimental mouthwash.

2 Planned Analyses

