4.4.1.2 Statistical Hypothesis, Model, and Method of Analysis

The primary analysis is a comparison of the mean change from baseline Schiff sensitivity score between Test Product and Negative Control at Week 8.

The null hypothesis for the primary endpoint is that the mean change from baseline in Schiff sensitivity score is equal between the two products.

$$H_0: \mu_1 = \mu_2$$

The alternative hypothesis is that the mean change from baseline in Schiff sensitivity score is not equal between the two products.

$$H_1: \mu_1 \neq \mu_2$$

The change from baseline in Schiff sensitivity score at Week 8 will be analyzed using ANCOVA with treatment as factor and mean baseline Schiff sensitivity score as covariate. Note that since the baseline Schiff sensitivity score will be included as a covariate, the baseline Schiff stratification value will not be included in the model. Adjusted means of all treatments and their SEs, P-value and 95% confidence interval (CIs) will be presented on the ITT population (Table 14.2.1.1.2). Treatment differences of the treatment comparisons will also be provided together with P-values and 95% CIs.

The assumption of normality and homogeneity of variance in the ANCOVA model will be investigated and if violated, data transformations will be investigated. If suitable transformations cannot be found, non-parametric Van Elteren tests will be performed adjusting for the maximum baseline Schiff sensitivity scores and results will be compared with the ANCOVA results. If the inferences from the two analyses are similar then both sets of results will be reported and emphasis will be made on the ANCOVA results. In case of discrepancies between p-values of ANCOVA and Van Elteren analysis, inferences will be drawn on the non-parametric analysis.

To visually inspect the treatment effect on Schiff sensitivity scores, a plot across time (Baseline, Week 4 and Week 8) will be displayed with raw means and SE bars. The plot will display a different symbol line for each treatment group (Figure 14.2.1).

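### Does SAP Section 1 let a favourable sign alone count as demonstrated efficacy?

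*SAP*

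**What the plan says.** SAP Section 1, headed as a summary of key protocol information, opens with "The purpose of this trial is to demonstrate the efficacy and safety of a 1.5% dipotassium oxalate monohydrate (KOX) containing oral rinse". It continues: "Efficacy will be demonstrated as a treatment difference in favour of the 1.5% KOX containing oral rinse vs. the negative control oral rinse". The sentence names the direction, the comparator, the outcome and the week. It gives no criterion in terms of a p-value, a confidence interval or a size of effect.

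The protocol is more reserved. Its synopsis (Brief Summary) says that the "method development study will be used to investigate the efficacy of an experimental oral rinse". Protocol 9.2.4, after naming the primary comparison, adds: "However a statistically significant difference is not expected as the study is not powered". It then says: "The magnitude of the treatment difference is more important and is expected to be in favour of the experimental mouthwash". No threshold for magnitude is given. SAP 1.4 repeats the sentence on magnitude but not the one on significance. SAP 1.2 states the primary objective neutrally, as evaluating and comparing efficacy.

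On inference, SAP 4.4.1.2 sets equality of the two mean changes against a two-sided alternative for Test Product and Negative Control at Week 8, and calls for ANCOVA with adjusted means, treatment differences, p-values and 95% confidence intervals. For the case where the ANCOVA assumptions fail and no transformation helps, it adds: "In case of discrepancies between p-values of ANCOVA and Van Elteren analysis, inferences will be drawn on the non-parametric analysis". The only explicit significance level in the SAP is in Section 1.4: "using a two-sided t-test of significance level 0.05 for the experimental product against the negative control".

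**The concern.** Section 1 is the one place in the SAP that says how efficacy is to be demonstrated, and it can be read as asking only for an estimate on the right side of zero. That reading has some support in the documents' vocabulary. Protocol 9.2.4 expects the difference to favour the experimental rinse in the same breath as it says significance is not expected. The footnote to the SAP's efficacy table template also uses favouring in the sense of sign alone. Section 1 and Section 4.4.1.2 do not refer to each other.

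At stake is the wording of the study report's conclusion. A small favourable estimate from a study its own protocol calls unpowered might be written up as efficacy demonstrated.

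**Working it through.** **Inputs, all from SAP 1.4 and protocol 9.1.** Evaluable subjects 40 / 20 / 20 (test, negative control, placebo), planning difference 0.36, SD 0.8, two-sided level 0.05.

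**The plan's own figures.** The standard error of a difference is SD × √(1/n₁ + 1/n₂), and power comes from the non-central t distribution.

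- Test against combined control, 40 v 40: SE = 0.8 × √(1/40 + 1/40) = 0.179, non-centrality 0.36/0.179 = 2.01, 78 degrees of freedom. Power is 51.1%, as the plan states.
- Test against negative control, 40 v 20: SE = 0.8 × √(1/40 + 1/20) = 0.219, non-centrality 0.36/0.219 = 1.64, 58 degrees of freedom. Power is 36.6%. The plan says "the study has less than 50% power to detect a mean treatment difference of 0.36 in the Schiff sensitivity score", which is true.

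**The two readings of Section 1, 40 v 20.** The sign-only reading is met with probability Φ(true difference / 0.219). The test-based reading needs a two-sided p below 0.05 in favour of the test rinse. The true differences 0, 0.10 and 0.20 are assumptions chosen to show the range; 0.36 is the plan's value.

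| True difference in favour | Favourable sign | Significant in favour |
|---|---|---|
| 0 | 50% | 2.5% |
| 0.10 | 68% | 6.5% |
| 0.20 | 82% | 14.4% |
| 0.36 | 95% | 36.5% |

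**Where they part.** The expected unadjusted 95% half-width is 0.44, so an observed difference must reach about 0.44 to be significant. An estimate equal to the planning value would have an interval from 0.36 + 0.44 = 0.80 in favour to 0.44 − 0.36 = 0.08 against. It would satisfy the sign-only reading and fail the test.

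Adjustment for baseline may narrow the interval, by the factor √(1 − r²). Here r is the correlation of baseline with change, which the documents do not give. Taking 0.8 as the SD of change and 76 error degrees of freedom for the three-arm ANCOVA, r = 0, 0.3 and 0.5 give half-widths of 0.436, 0.416 and 0.378 and power of 36.8%, 39.8% and 46.6%.

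**Which text governs.** Set side by side, the two sections concern the same comparison, outcome and week.

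- Section 1 is a summary paragraph. It specifies no analysis and no output.
- Section 4.4.1.2 specifies hypotheses, model, p-value and 95% interval, and settles a conflict between two analyses by their p-values. If sign decided, none of that would be needed.
- The 95% intervals correspond to the 0.05 level in Section 1.4, so the level does not have to be invented.

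An analyst following 4.4.1.2 reports the difference with its interval and p-value whatever Section 1 says. The contrast in the table arises only for a report that disregards 4.4.1.2.

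**The case for a change.** The strongest case for a change is that the ambiguity bites in the plan's own expected case: an observed 0.36 would be favourable and not significant. Section 1 is offered as a summary of the protocol yet speaks of demonstrating where the protocol investigates. SAP Section 5, which lists departures from the protocol, mentions only the per-protocol rule. Section 4.4.1.2 states neither a level nor a rule for declaring efficacy, and because protocol 9.2.4 plays significance down, one cannot be sure that a report writer would fall back on the test. Rewriting a few sentences would cost little.

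What stands is the difference in tone: Section 1 is more confident than the protocol and than SAP 1.2, and a cross-reference would have been tidier. The rest does not carry a change. An estimate of 0.36 would appear beside an interval that crosses zero, in a study whose protocol says in advance that significance was not expected, so a reader could see what had and had not been shown. A rule tying efficacy wording to p below 0.05 would add a gate that the protocol does not contain and that sits uneasily with its ranking of magnitude above significance. Stating power as about 37% would only refine a true statement, and it would have to be made in the protocol synopsis, protocol 3.3, protocol 9.1 and SAP 1.4 together.

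**Conclusion.** No change follows. The calculations are sound: 50% against 2.5% under no effect, and 95% against 36.5% at 0.36, for an unadjusted comparison of 40 with 20 and an SD of 0.8. They measure the consequence of reading one introductory sentence without the section that specifies the analysis. Read together, SAP 1.2, 1.4 and 4.4.1.2 and protocol 9.2.4 supply a neutral objective, a two-sided test, the 0.05 level used in planning, 95% intervals and the warning about power. No estimate, interval, p-value, population or output depends on the Section 1 sentence. What remains is loose wording that analysts and report writers will resolve from those sections. This conclusion assumes that the report presents the Week 8 difference with its interval and p-value, as SAP 4.4.1.2 requires.
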